#### 7.1.2. Start of infusion with the Investigational Product

Infusion of the Investigational Product will start approximately 12hrs (6-18hrs) before the anticipated time of islet infusion. The Investigator will identify the time to start study drug infusion. Infusion may be halted during pancreatic surgery if required, provided that interruption is not longer than 6 hours.

The infusion pump will be set to provide the infusion rate corresponding to the planned dose. Infusion rate (mL/hour) corresponding to each unit increment (kg) of body weight, is reported in **Appendix 14.3**.

Immediately before the start of infusion, the removable label on the Infusion Bag No. 1 will be detached and attached to the relevant page of the CRF. Starting time of drug administration and infusion rate will be recorded in the CRF.

### 7.1.3. Islet isolation and transplantation

Techniques for pancreas removal will be used, as per centre practice, including requirement for concomitant splenectomy.

Islet preparation: Site will process islets by enzymatic digestion using an FDA approved collagenase and neutral protease as per site specific standards. The pancreas will be distended by intraductal infusion of collagenase/neutral protease; if duct disruption prohibits intraductal infusion, enzyme will be manually injected into the pancreatic parenchyme. Pancreatic digestion will be performed using the semi-automated method of Ricordi. Purification will be performed when necessary to reduce tissue volume, dependent on site specific standards for islet manufacturing, using density centrifugation with COBE 2991. Samples will be taken from the pancreatic preservation solution and final islet product for sterility testing by gram stain and culture.

Islet mass will be assessed by manual counts as detailed in **Appendix 14.6.1** and quantified as total IEQ and IEQ/kg body weight. The final product is suspended in a 200 mL suspension of CMRL 1066 Transplant Media or equivalent solution. The final product is supplied in one to three 200 mL infusion bags, containing a minimum dose of >10,000 IEQ total.

Islet infusion: At all sites, islets will be transplanted on the same day as the total pancreatectomy procedure.

The islet mixture will be delivered slowly by gravity drainage into the portal vein or a tributary of the portal vein. Access to the portal vein may be obtained by direct cannulation during laparotomy or by percutaneous access by fluoroscopic, ultrasonographic, or real-time CT guidance.

At minimum, portal venous pressure will be monitored (direct venous measurement) before initiation, mid-way, and after completion of islet infusion. In case the portal pressure reaches >35 cmH2O, islet infusion will be put on hold, and restarted when portal pressure has dropped. In the rare event that portal pressure does not lower (within a 30 min interval), infusion is definitely stopped and any remaining tissue either discarded or placed in another tissue (e.g. peritoneal cavity, duodenal wall, underneath the kidney capsule, etc.).

The following isolation and operative details will be recorded in the CRF, as per documentations provided by the local Islet Processing Facility and centre information:

- Date and time of isolation (procedure completed);
- Date and time of infusion (start and end of infusion);
- IEQ/kg infused. Islet will be counted as detailed in **Appendix 14.6.1**;
- Total islet infusion volume;
- Pre-, mid-way, and post- infusion portal pressure.

#### **7.1.4. Drug administration during hospital stay**

Administration of the Investigational Product will continue during hospital stay.

Infusion Bags will be used in a sequential manner (No. 1, No. 2, No. 3 etc.) and infusion of the Investigational Product will progress non-stop up to a total of 7 day (168hrs) administration.

The removable label on each new Infusion Bag will be detached and attached to the relevant page of the CRF. Start date/time and stop date/time for each Bag will be recorded in the CRF, along with accidental interruptions of study drug infusion for > 30min (cumulative within each 24 hours).

#### **7.1.5. Post-operative assessments**

The following will be assessed during hospital stay and recorded in the CRF. Measurement will be performed as per centre practice, unless otherwise specified.

- Renal function (Clcr, urine output): Renal function will be assessed daily from post-operative day 1 up to the end of study drug infusion. Details of Clcr calculation are reported in **Appendix 14.6.2**. There is no need to have a urine catheter in place, if this is not required by standard of care. Urine volume will be measured at urination (measuring cylinder); corresponding collection time will be calculated from the previous urination. Depending from feasibility and patient compliance, ideally more than one measurement should be done over a 24-hour period to get the best estimate of urine output.
- Total bilirubin: Total bilirubin will be assessed daily from post-operative day 1 up to the end of study drug infusion as part of hepatic function evaluation.
- XDP, ALT/AST, INR/PTT, C-reactive protein (CRP): These will be measured daily from day 1 up to day 7 post-transplant.
- Chemokines/cytokines [CXCL8, CCL2 (MCP-1), CCL3, CCL4, CXCL10 (IP-10), CXCL9 (MIG), IL-6, IL-10, INF- $\gamma$ , TNF- $\alpha$ , and IL-1 $\beta$ ]: A blood sample will be obtained @ 6, 12, 24, 72, 120 and 168hrs after the end of islet infusion. Samples will be handled and stored for the centralized assay, as detailed in **Appendix 14.6.3**.
- miR-375: A blood sample will be obtained @ 6, 12, 24, 72, 120 and 168hrs after the end of islet infusion. Samples will be handled and stored for the centralized assay, as detailed in **Appendix 14.6.3**.
- Pharmacokinetics [plasma levels of reparixin (total and unbound) and relevant metabolites (DF2243Y and ibuprofen)]: A blood sample will be obtained in all patients randomized and treated with the Investigational product on post-operative day 1, 3 and 5, ideally in the morning. In a subset of at least 20-24 patients, treated at 2 selected sites, a blood sample will be also obtained just prior to, and then at 1, 3, 5, 6, 8, and 12 hrs after termination of Investigational Product administration. Samples will be handled and stored for centralized assay, as detailed in **Appendix 14.6.3**.
- Safety laboratory tests: Laboratory tests will be performed before hospital discharge.
- Vital signs, i.e. blood pressure (BP) and heart rate (HR) will be measured before hospital discharge.

During hospital stay, all AEs (see details in Sections 8.2.) and CMEDs (see details in Sections 6.5.) will be recorded.

For all measurements above, the actual date and time of assessment, including date of sampling, will be recorded in the CRF.

Apart from compliance with protocol procedures up to day 7 post-transplant, hospital discharge will be primarily based on criteria related to total pancreatectomy (the major surgical procedure in total pancreatectomy followed by IAT) and will comply with each site's hospital standards. However, at all sites, at least the following criteria will be complied with: "A patient will be discharged if he/she at least is ambulating, has adequate nutrition (oral, enteral, or Total Parenteral Nutrition (TPN), is not requiring any intravenous medications which require inpatient monitoring, pain is adequately treated, and he/she has a stable plan for glycemic control (management of blood glucose testing and insulin administration at home)".

## 7.2. FOLLOW-UP PROCEDURES AND ASSESSMENTS

Since hospital discharge, patients will self monitor glucose levels and insulin intake according to standard clinical instructions at the site. Insulin will be administered to target fasting and pre-meal glucose levels in the range 80-125 mg/dL, and 2 hour post-prandial glucoses <180 mg/dL. For patients on continuous enteral or parental feeds, insulin will be titrated to maintain glucose in the range 80-140 mg/dL.

The Investigator will identify if- and the date when- it is appropriate for the patient to stop insulin intake, according to standard of centre practice. Regardless the patient is on or off insulin, he/she will report on a Diary Card (see **Appendix 14.7**) his/her self monitored glucose levels for 14 consecutive days prior to the follow-up visits on day  $75 \pm 14$  and  $365 \pm 14$  after the transplant: glucose levels will be measured at least two times a day: 1) after an overnight fast (or anyway before breakfast if the patient is still on a tube feed and TPN); 2) within 2 hours post-prandial. Also, patients still on insulin will report on the Diary Card their daily insulin intake.

Patients will attend the centre for study assessments on 2 follow-up visits scheduled on day  $75 \pm 14$  and  $365 \pm 14$  after the transplant.

At each **visit**, the following will be evaluated/measured in all patients as per centre practice, unless otherwise specified. Measurements, including the actual date and time of assessment, or the date of sampling, will be recorded in the CRF.

- Patient weight.
- Retrospective self-measured glucose and insulin requirement data in the 2 weeks prior to the visit will be reviewed and average (previous week) insulin requirement at each time point as well as insulin-independence / insulin-dependence status will be assessed.
- Retrospective episodes of severe hypoglycaemia in the interval will be assessed as per centre practice. Events of documented hypoglycemia in the interval will be obtained from review of the patient's home glucometer download from between visits and/or patient glucose logs.
- Retrospective severity of steatorrhea in the 4 weeks prior to the visit will be evaluated.
- A blood sample will be taken prior to the meal administration to measure HbA1c, albumin and pre-albumin. ALT/AST will be also measured on day  $75 \pm 5$ .
- A MMTT test will be performed as detailed in **Appendix 14.6.4**. Blood samples will be drawn @ 0 (2 basal samples in the range between -20 to 0 prior to the meal) and 15, 30, 60, 90, 120, 180, 240 min after the meal for glucose, C-peptide and insulin measurement.
- $\beta$ -score will be calculated according to *Ryan (2005)* (see **Appendix 14.6.5** for details).

C-peptide and HbA1c will be measured by a centralized laboratory with CLIA certification and National Glycohemoglobin Standardization Program (NGSP) certified assay. Details of handling and storage of samples as well as data handling are reported in **Appendix 14.6.3**.

Any SAEs that occurred after hospital discharge will be recorded at the visits, as well as CMEDs, as appropriate.

Patients should be strongly motivated to attend the centre for the planned follow-up visits. However, if a patient cannot refer to the site for protocol assessments, the Investigator will try to obtain any relevant information from the patients, including documents/lab results available from local medical care.

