### 4.2. STUDY ENDPOINTS

#### 4.2.1. Primary efficacy endpoint

- The proportion of insulin-independent patients following IAT [time frame: day 365±14 after the transplant].

For the purpose of this protocol, insulin-independence is defined as freedom from the need to take exogenous insulin for 14 or more consecutive days, with adequate glycemic control, as defined by:

- a glycated hemoglobin (HbA1c) level  $\leq 6.5\%$ ;
- fingerstick fasting blood glucose not exceeding 126 mg/dL more than three times in the past week (based on a minimum of one daily measurement);
- a 2 hour post-prandial blood glucose not exceeding 180 mg/dL more than four times in the past week (based on a minimum of one daily measurement);
- a laboratory fasting glucose in the non-diabetic range ( $<126$  mg/dL).

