#### 14.7. APPENDIX 7 – SAMPLE DIARY CARD

Clinical Trial REP0112	PATIENT DIARY CARD						PATIENT No.    
Sponsor: Dompé s.p.a.							

Please report in the table below your blood glucose (fingerstick) for 14 days before the planned follow-up visit. You are required to report at least one value taken after an overnight fast (or anyway before breakfast) and one value taken within 2 hours after one of the two meals. Also, please report the total amount of insulin you have taken each day.
 
Please add the date as day/month/year (example 25/07/2012 for 25 July 2012) and the time as 24 hours clock (example 9.35 in the morning, 21.35 in the afternoon). Please enter the information requested with indelible ink.
							
Day	Breakfast glucose		Lunch glucose		Dinner glucose		Daily Insulin
	Time	Value Before	Time	Value After	Time	Value After	
Monday - date:							
Tuesday - date:							
Wednesday - date:							
Thursday - date:							
Friday - date:							
Saturday - date:							
Sunday - date:							

Investigator's signature: \_\_\_\_\_ date: \_\_\_\_\_

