Notes: Plots for mean values  $\pm$  standard error bars will be presented for each treatment group at each time point (where “Basal” is the single baseline which is the average of the two basal values). Each treatment group will be in a different color with an accompanying legend. Separate pages will be created for CXCL8 (pg/mL), CCL2 (MCP-1) (pg/mL), CCL3 (pg/mL), CCL4 (pg/mL), CXCL10 (IP-10) (pg/mL), CXCL9 (MIG) (pg/mL), IL-6 (pg/mL), IL-10 (pg/mL), INF- $\gamma$  (pg/mL), TNF- $\alpha$  (pg/mL), and IL-1 $\beta$  (pg/mL).

Dompé farmaceutici S.p.A  
Protocol REP0112

Page X of Y

Figure 14.4.15.1 miR-375, Plots of Mean Values Over Time – Safety Population

X-axis: Time Point (Pre-transplant 1, 6 Hours Post, 12 Hours Post, 24 Hours Post, 72 Hours Post, 120 Hours Post, and 168 Hours Post)

Y-axis: miR-375 (copies/mL), mean  $\pm$  standard error

Reference: 14.3.13, 16.2.15

Notes: Plots for mean values  $\pm$  standard error will be presented for each treatment group at each time point. Each treatment group will be in a different color with an accompanying legend.

Dompé farmaceutici S.p.A  
Protocol REP0112

Page X of Y

Listing 16.2.6.1.1 Insulin Independence, Alternative Definition

Treatment: Reparixin or Placebo

Patient Number	Visit	Date (Day) of Visit	Insulin Ind, Alternative Definition
XXXX	Day 365	DDMMMYYYY (XXX)	Yes
XXXX	Day 365	DDMMMYYYY (XXX)	Yes
XXXX	Day 365	DDMMMYYYY (XXX)	Yes
.	.	.	.
.	.	.	.
.	.	.	.

Reference: CRF Page 24 and 24.1 and listings 16.2.6.2, 16.2.6.3.1 and 16.2.6.4.

Notes: Ind = Independent. Alternative definition: freedom from the need to take exogenous insulin for 14 or more consecutive days; a glycated hemoglobin (HbA1c) level  $\leq$  6.5%; a laboratory fasting glucose in the non-diabetic range ( $<126$  mg/dL); and a 90 minute blood glucose not exceeding 180 mg/dL from the MMTT. This measure is proposed as an alternative to finger-stick 2-hour post-prandial glucose on patient diary.

Dompé farmaceutici S.p.A  
Protocol REP0112

Page X of Y

Listing 16.2.6.3 Mixed Meal Tolerance Test, C-peptide Area Under the Curve (AUC), Alternative Computation

Treatment: Reparixin or Placebo								
Patient Number	IEQ/kg Infused During IAT	Visit	Mixed Meal Administration Date (Day)	End Time	Time Point	Sample Time	C-peptide (ng/mL)	Area Under the Curve (unit)
XXXX	XXXXX	Day XXX	DDMMMYYYY (XXX)	HH:MM	Basal 1	HH:MM	X.XX	XXX.X
					Basal 2	HH:MM	X.XX	
					Basal	HH:MM	X.XX	
					15 min	HH:MM	X.XX	
					30 min	HH:MM	X.XX	

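### The primary endpoint judges a 2-hour post-prandial glucose, but Section 7.2 and the diary card accept any reading within 2 hours and record no meal time, so off-time readings can count and cannot be identified

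*Protocol*

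**What the plan says.** Protocol 4.2.1 makes insulin independence conditional on several glycemic criteria. One is "a 2 hour post-prandial blood glucose not exceeding 180 mg/dL more than four times in the past week". At least one such reading a day is required. SAP 4.1 repeats the criterion without a timing tolerance.

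The data come from the patient's diary. Protocol 7.2 asks for two glucose values a day over the 14 days before each follow-up visit: one fasting, and one "within 2 hours post-prandial". The card in Protocol Appendix 7 asks for "one value taken within 2 hours after one of the two meals". It wants the date "and the time as 24 hours clock", and has one time column beside each glucose value.

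These values feed the endpoint directly. Under Protocol 7.2, "Retrospective self-measured glucose and insulin requirement data in the 2 weeks prior to the visit will be reviewed", and insulin-independence status is assessed from that review.

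The SAP addendum (note to Listing 16.2.6.1.1) also lists an alternative definition of insulin independence. It uses "a 90 minute blood glucose not exceeding 180 mg/dL from the MMTT" and drops the diary glucose criteria. Of this it says: "This measure is proposed as an alternative to finger-stick 2-hour post-prandial glucose on patient diary".

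**The concern.** A value at 2 hours and a value at any point up to 2 hours are different measurements. The definition requires the first; the instruction and the card accept the second. A patient who follows the card exactly may supply readings that the definition does not describe, and the site then counts them against 180 mg/dL.

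This cannot be put right at analysis. With a single clock time per value, the elapsed time since the meal is not recoverable. At stake is the classification of individual patients on the primary endpoint, since failing this one component makes a patient a failure.

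**Working it through.** **1. The texts side by side**

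| Place | Timing of the post-prandial value |
|---|---|
| Protocol 4.2.1 and SAP 4.1 (definition) | 2 hours |
| Protocol 7.2 (insulin target) | 2 hours |
| Protocol 7.2 (diary instruction) | within 2 hours |
| Protocol Appendix 7 (card) | within 2 hours |
| Protocol Appendix 5 (time windows) | windows for MMTT samples (±5 or ±10 minutes), none for diary glucose |
| SAP | no window and no rule for off-time readings |

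No text reconciles the two wordings.

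**2. The plan's own design figure**

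Inputs from Protocol 9.1: 23% vs 55%, one-sided 0.025, 90% power. With unpooled variance, n = (1.960 + 1.282)² × (0.23×0.77 + 0.55×0.45) / 0.32² = 43.6, so 44 per arm. This reproduces the plan. The pooled-variance formula gives 88.2% power at 44 per arm, and the exact power of the Pearson chi-square is 88.8%, inside the stated 87-90%.

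**3. How much the four-exceedance allowance absorbs**

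Failing the component needs at least 5 readings above 180 mg/dL in the week. Let q be the chance that one reading exceeds the limit, with readings assumed independent. Then P(fail) = P(X ≥ 5), X ~ Binomial(m, q). The minimum is m = 7. If lunch and dinner values are both recorded daily, m = 14.

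| q | m = 7 | m = 14 |
|---|---|---|
| 0.2 | 0.5% | 13% |
| 0.4 | 9.6% | 72% |
| 0.6 | 42% | 98% |
| 0.8 | 85% | >99% |

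Read in reverse, a 5%, 10% or 20% chance of failing needs q of about 34%, 40% or 48% with 7 readings, but only about 15%, 19% or 23% with 14. The allowance covers isolated off-time readings. It does not cover a steady habit of off-time testing that often exceeds the limit, and it protects less when more values are recorded.

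**4. What misclassification would cost (illustration only)**

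The documents give no misclassification rate, so 5%, 10% and 20% are assumed, equally in both arms. If a share s of true successes is counted as failures, each success rate is multiplied by (1 − s). For example, s = 10% turns 23% vs 55% into 20.7% vs 49.5%, and the difference shrinks from 32 to 28.8 points.

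The stratified figures come from simulating the Cochran-Mantel-Haenszel test at N = 100, 1:1, one-sided 0.025. The Protocol 9.1 rates were used (13% vs 40%, 23% vs 55%, 55% vs 84%). With the 34/42/24% stratum mix of the recent series in 9.1, and also with half the patients in the middle stratum, results agree within about one point.

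| True successes lost | CMH, N = 100 | Unstratified, 44 per arm |
|---|---|---|
| 0% | about 89-90% | 88.2% |
| 5% | about 86% | 85.2% |
| 10% | about 83% | 81.9% |
| 20% | about 75% | 74.5% |

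The opposite error also costs power. If 5%, 10% or 20% of true failures were counted as successes, power at 44 per arm would be 83.5%, 78.5% or 67.6%.

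**The case against.** The strongest reply is that the mismatch may do little in practice. A reading at 2 hours satisfies both wordings. Protocol 7.2 leaves self-monitoring to each site's standard instructions and sets the insulin target on 2-hour values, so many patients may already test at 2 hours. Four exceedances a week are forgiven. With the minimum seven readings, a patient needs a per-reading exceedance chance of about 34% before failing even 5% of the time, and the patients concerned must be off insulin with HbA1c at or below 6.5%. All of this stands, and it limits the likely size. It does not remove the contradiction or make off-time readings detectable, and reliance on site instructions means that timing may differ between sites.

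Three stronger readings are tempting, and the documents do not support them.

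- A reader might infer that true successes are being turned into failures because early readings run higher. No text gives the glucose course after home meals, and the instruction also admits very early readings, so the direction is open.
- A reader might infer a bias towards one arm. The trial is double-blind and the instruction is common to both arms, so non-differential error is the reasonable expectation.
- A reader might infer that the addendum repeats the mistake by using the 90-minute MMTT value although a 120-minute sample is drawn. The addendum presents it openly as an alternative, and addendum Section 3.1 labels its efficacy endpoints exploratory. Choosing another time point there is not an error. Because that definition does not use diary glucose, it even offers a partial check on this problem.

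**Conclusion.** The inconsistency is real and affects a component of the primary endpoint: the definition needs a 2-hour value, the collection instruction does not require one, and the card cannot show which was obtained. Followed as written, the plan lets off-time readings decide a patient's status unseen.

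The size cannot be determined from the documents. The power losses above rest on assumed rates of 5%, 10% and 20%, applied at random and equally in both arms, and on the effect sizes in Protocol 9.1. They show what misclassification would cost if it occurred, not that it occurs. The expected consequence is a diluted comparison with some loss of power. The planned sample size calculation itself is unaffected.

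**What to change.** 1. Reconcile Protocol 7.2 and the Appendix 7 card with 4.2.1, so that the diary asks for the 2-hour value. The sponsor should state whether the 2 hours run from the start or the end of the meal; Section 4.2.1 is silent on this.
2. Add a meal-time field to the card for every Day 365 diary still to be completed. When the amendment that raised the cap at the lead site was written, 86 of the planned 100 patients had been transplanted, so at least 14 transplants, and their Day 365 diaries, were still to come.
3. Pre-specify in the SAP a timing window for the diary value and a rule for readings outside it or without a meal time.
4. Flag diaries completed under the present instruction, and show the primary result with and without those patients.

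The 90-minute value in the addendum's alternative definition can stay.

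The cost is a wording change, one diary field and one short SAP rule. Completed diaries cannot be repaired. The small downside is that early and late patients will have had different instructions within one endpoint. Block randomization within centre should keep that split roughly even between arms, and the flag in step 4 makes it visible.

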### **7.3. EARLY PATIENT WITHDRAWAL**

#### **7.3.1. Criteria for withdrawal from the study**

Patients will be informed that they have the right at any time to withdraw from further participation in the study (*withdrawal of consent*), without prejudice to their medical care, and without being obliged to state their reasons. However, during the consent process, patients will be also educated about the scientific relevance of their continued participation as well as the deleterious effect that missing data will have on trial integrity.

If a patient fails to return to the centre for a scheduled visit, all reasonable attempts should be made to contact the patient to ensure that the reason for not returning is not a SAE. Likewise if a patient declares his/her wish to discontinue from the study e.g. for personal reasons, an attempt should be made to establish that the true reason is not a SAE (bearing in mind the patient is not obliged to state his/her reasons). The term *withdrawal of consent* should be used only when the patient no longer wishes to participate in the trial and no longer authorizes the Investigators to make efforts to continue to obtain his/her outcome data. Ideally, if patients withdraw their consent, it should be done in writing.

Patients who have discontinued the study treatment should be anyway followed to ensure that primary and secondary outcome measures are assessed, unless they formally have withdrawn consent.

It is important that any randomized patient remains in the study and is followed for both efficacy and safety outcomes, regardless he/she has completed or discontinued the study treatment. Investigators will be trained about the importance of patient retention and full data capture. Also, all reasonable attempts should be made by the Investigators to emphasize continued patient's participation for the full duration of the trial.

Any withdrawals must be fully documented in the CRF.

